	
 5. Known brain metastases that are ≥ 10mm or cranial epidural disease unless adequately treated with radiosurgery and/or surgery (including radiosurgery). Eligible subjects must be neurologically asymptomatic and without corticosteroid requirement. Dexamethasone ≤ 2mg daily (or equivalent) will be allowed if discontinuation of corticosteroids is not feasible due to post-radiation effects and patient is asymptomatic. Patients with active, asymptomatic brain metastases that are < 10mm and no corticosteroid requirement will be allowed without radiosurgery or surgery. 6. History of active autoimmune disorder requiring immunosuppressive agents. Patients with autoimmune disorders considered low risk, such as vitiligo and thyroiditis, will be allowed. 7. Concomitant anticoagulation with coumarin agents (eg, warfarin), direct thrombin inhibitors (e.g., dabigatran), betrixaban, or platelet inhibitors (eg, clopidogrel). Allowed anticoagulants are the following: 
 a. Prophylactic use of Low-dose aspirin for cardio-protection (per local applicable guidelines) and low-dose low molecular weight heparins (LMWH) are permitted. b. Anticoagulation with therapeutic doses of LMWH or anticoagulation with direct factor Xa inhibitors rivaroxaban, edoxaban, or apixaban is allowed in subjects without known brain metastases who are on a stable dose of the anticoagulant for at least 1 week before first dose of study treatment, and who have had no clinically significant hemorrhagic complications from the anticoagulation regimen or the tumor. 8. The subject has prothrombin time (PT)/INR or partial thromboplastin time (PTT) test $\geq 1.3 \times$ the laboratory ULN within 7 days before the first dose of study treatment. 9. The subject has uncontrolled, significant intercurrent or recent illness. 10. Major surgery (eg, GI surgery, removal or biopsy of brain metastasis) within 8 weeks before first dose of study treatment. 11. Corrected QT interval calculated by the Fridericia formula (QTcF) > 500 ms per electrocardiogram (ECG) within 28 days before first dose of study treatment. 12. Pregnant or lactating females. 13. Inability to swallow tablets. 14. Previously identified allergy or hypersensitivity to components of the study treatment formulations. 15. Diagnosis of another malignancy within 2 years before first dose of study treatment, except for superficial skin cancers, or
--	---

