5.0 STUDY DESIGN

5.1 Overall Schema

Subjects with unresectable advanced melanoma meeting eligibility criteria (refer to Section 6.0) will be screened for participation on the protocol. The screening phase will include obtaining baseline imaging studies, labs, history & physical, EKG, and collection of a fresh tumor biopsy or archived tumor specimen (refer to Table 7-1). Once meeting eligibility criteria and enrolled on study, subjects will begin treatment with nivolumab/ipilimumab and cabozantinib starting on day 1 of cycle 1. The treatment schedule and follow up is outlined further in the schema Figure 5-1 and Table 7-1. Patients who attain confirmed response or stable disease and are able to tolerate study drugs will continue treatment for up to 2 years. Discontinuation after 1 year but prior to 2 years will be permitted at the discretion of the treating investigator in patients with disease control achieving either a complete or partial response.

Figure 5-1. Treatment Schema

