6.0 INCLUSION/EXCLUSION CRITERIA

To be eligible for the study the subject must meet all of the inclusion and none of the exclusion criteria:

Inclusion Criteria

1. All patients must have unresectable stage IIIb-IIIId or IV melanoma by AJCC 8th edition.
Note: Patients with uveal melanoma are excluded from this study.
2. Age \geq 18 and ECOG Performance Status of 0 or 1.
3. Measurable disease by imRECIST.
4. Baseline tumor specimen available – either archived tumor specimen collection within the past year and no intervening treatment or fresh tumor collection (A waiver may be considered for the baseline biopsy requirement after discussion with study principal investigator).
5. Recovery to baseline or \leq Grade 1 CTCAE v4 from toxicities related to any prior treatments, unless AE(s) are clinically nonsignificant and/or stable on supportive therapy.
6. Adequate organ and marrow function, based upon meeting all of the following laboratory criteria within 14 days before first dose of study treatment:
 - a. Absolute neutrophil count (ANC) \geq 1500/mm³ (\geq 1.5 GI/L) without granulocyte colony-stimulating factor support.
 - b. White blood cell count \geq 2500/mm³ (\geq 2.5 GI/L).
 - c. Platelets \geq 100,000/mm³ (\geq 100 GI/L) without transfusion.
 - d. Hemoglobin \geq 9 g/dL (\geq 90 g/L).
 - e. Alanine aminotransferase (ALT), aspartate aminotransferase (AST), and alkaline phosphatase (ALP) \leq 3 \times upper limit of normal (ULN). ALP \leq 5 \times ULN with documented bone metastases.
 - f. Total bilirubin \leq 1.5 \times ULN (for subjects with Gilbert's disease \leq 3 \times ULN).
 - g. Serum albumin \geq 2.8 g/dl.
 - h. Serum creatinine \leq 2.0 \times ULN or calculated creatinine clearance \geq 30 mL/min (\geq 0.5 mL/sec) using the Cockcroft-Gault equation:
Males: $(140 - \text{age}) \times \text{weight (kg)} / (\text{serum creatinine [mg/dL]} \times 72)$
Females: $[(140 - \text{age}) \times \text{weight (kg)} / (\text{serum creatinine [mg/dL]} \times 72)] \times 0.85$
 - i. Urine protein/creatinine ratio (UPCR) \leq 1 mg/mg (\leq 113.2 mg/mmol).
7. Capable of understanding and complying with the protocol requirements and must have signed the informed consent document.

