8. Sexually active fertile subjects and their partners must agree to use medically accepted methods of contraception (eg, barrier methods, including male condom, female condom, or diaphragm with spermicidal gel) during the course of the study and for 4 months after the last dose of study treatment.
9. Female subjects of childbearing potential must not be pregnant at screening. Females of childbearing potential are defined as premenopausal females capable of becoming pregnant (ie, females who have had any evidence of menses in the past 12 months, with the exception of those who had prior hysterectomy). However, women who have been amenorrheic for 12 or more months are still considered to be of childbearing potential if the amenorrhea is possibly due to prior chemotherapy, antiestrogens, low body weight, ovarian suppression or other reasons.

Exclusion Criteria

1. Prior treatment with anti-PD-1/PD-L1 therapy, anti-CTLA-4 therapy or cabozantinib. Prior adjuvant anti-PD-1 and/or anti-CTLA-4 therapy is allowed if relapse is greater than 6 months from last dose.
2. Receipt of any type of small molecule kinase inhibitor (including investigational kinase inhibitor) within 2 weeks before first dose of study treatment.
3. Receipt of any type of cytotoxic, biologic or other systemic anticancer therapy (including investigational) within 4 weeks before first dose of study treatment.
4. Radiation therapy for bone metastasis or brain metastasis within 2 weeks, any other radiation therapy within 4 weeks before first dose of study treatment. Systemic treatment with radionuclides within 6 weeks before the first dose of study treatment. Subjects with clinically relevant ongoing complications from prior radiation therapy are not eligible.

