5. Known brain metastases that are ≥ 10 mm or cranial epidural disease unless adequately treated with radiosurgery and/or surgery. Patients with treated brain metastases need to be asymptomatic (no neurologic symptoms or stable neurologic deficit) and off corticosteroids prior to start of treatment. If discontinuation of corticosteroids is not feasible due to post-radiation effects, asymptomatic patients on a stable dose of dexamethasone ≤ 2 mg daily (or equivalent) for ≥ 1 week prior to start of treatment will be permitted. Patients with active, asymptomatic brain metastases that are < 10 mm and no corticosteroid requirement will be permitted without radiosurgery or surgery based on nivo/ipi brain metastasis response data from Checkmate 204 [31]. Patients with active untreated brain metastases who are enrolled will require more frequent brain monitoring while on protocol. Refer to study schedule Table 7-1.
6. History of active autoimmune disorder requiring immunosuppressive agents. Patients with autoimmune disorders considered low risk, such as vitiligo and thyroiditis, will be allowed.
7. Concomitant anticoagulation with coumarin agents (e.g., warfarin), direct thrombin inhibitors (e.g. dabigatran), betrixaban, or platelet inhibitors (eg, clopidogrel).
Allowed anticoagulants are the following:
 - a. Prophylactic use of Low-dose aspirin for cardio-protection (per local applicable guidelines) and low-dose low molecular weight heparins (LMWH) are permitted.
 - b. Anticoagulation with therapeutic doses of LMWH or anticoagulation with direct factor Xa inhibitors rivaroxaban, edoxaban, or apixaban is allowed in subjects without known brain metastases who are on a stable dose of anticoagulant for at least 1 week before first dose of study treatment, and who have had no clinically significant hemorrhagic complications from the anticoagulation regimen or the tumor.
8. The subject has prothrombin time (PT)/INR or partial thromboplastin time (PTT) test $\geq 1.3 \times$ the laboratory ULN within 7 days before the first dose of study treatment.
9. The subject has uncontrolled, significant intercurrent or recent illness including, but not limited to, the following conditions:
 - a. Cardiovascular disorders:
 - i. Congestive heart failure New York Heart Association Class 3 or 4, unstable angina pectoris, serious cardiac arrhythmias.

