8.2.4.1.3 Hemorrhage

Hemorrhagic events, including serious and sometimes fatal events, have been reported with cabozantinib. Subjects should be monitored for bleeding events with serial complete blood counts and physical examination while on study.

Risk factors for hemorrhagic events may include (but may not be limited to) the following:

- Tumor of the lung with cavitory lesions or tumor lesions which invade or encase major blood vessels. NSCLC with squamous cell differentiation is known for significant lung cavitations and centrally located tumors that may invade major blood vessels. Thus, the anatomic location and characteristics of tumor as well as the medical history should be carefully reviewed in the selection of subjects for treatment with cabozantinib.
- Recent or concurrent radiation to the thoracic cavity.
- Active peptic ulcer disease, inflammatory GI diseases including Crohn's disease and ulcerative colitis.
- Underlying medical conditions which affect normal hemostasis (eg, deficiencies in clotting factors and/or platelet function, or thrombocytopenia).
- Concomitant medication with anticoagulants or other drugs which affect normal hemostasis.
- History of clinically significant hemoptysis, hematemesis, or hematuria.

The risk of hemorrhage in cabozantinib-treated subjects with brain metastases has not been thoroughly analyzed. Though the incidence of CNS hemorrhage events in a study of subjects with glioblastoma was higher than observed in general population of subjects with cancer treated with cabozantinib, it is not clear how the risk of hemorrhage in glioblastoma translates to a risk of hemorrhage for subjects with brain metastases. Currently, brain metastases of carcinomas are not contraindications to the use of cabozantinib, but subjects with brain metastases should be monitored with a high index of suspicion if symptoms that could be due to a CNS hemorrhage occur.

Complete healing from radiation-induced side effects should have occurred before initiating cabozantinib treatment, and cabozantinib should be discontinued in subjects with serious and life-threatening bleeding events or recent hemoptysis (≥ 2.5 mL of red blood).

Cabozantinib should be discontinued in subjects with serious and life-threatening bleeding events or recent hemoptysis (≥ 2.5 mL of red blood).

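### Exclusion 5 admits subjects whose post-radiation effects still need dexamethasone, while Section 8.2.4.1.3 says radiation effects should have healed completely before cabozantinib and makes no exception for them

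*Combined protocol and SAP*

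**What the plan says.** **Entry.** Section 6.0, exclusion 5, requires subjects with treated brain metastases to be asymptomatic and off corticosteroids before treatment starts, and then makes an allowance: "If discontinuation of corticosteroids is not feasible due to post-radiation effects, asymptomatic patients on a stable dose of dexamethasone" of no more than 2 mg daily (or equivalent), held for at least one week, are permitted. The synopsis version first states "Eligible subjects must be neurologically asymptomatic and without corticosteroid requirement", and its next sentence adds that the same low dose "will be allowed if discontinuation of corticosteroids is not feasible due to post-radiation effects and patient is asymptomatic". The synopsis does not repeat the one-week condition.

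**Other entry criteria that touch the same subject.** Exclusion 4 in Section 6.0 ends: "Subjects with clinically relevant ongoing complications from prior radiation therapy are not eligible". The synopsis version of exclusion 4 omits that sentence. Inclusion 5 asks for recovery from the toxicity of prior treatment, "unless AE(s) are clinically nonsignificant and/or stable on supportive therapy". The criteria apply jointly: "To be eligible for the study the subject must meet all of the inclusion and none of the exclusion criteria".

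**Start of cabozantinib.** Section 5.1 says "subjects will begin treatment with nivolumab/ipilimumab and cabozantinib starting on day 1 of cycle 1". Section 8.2.4.1.3 says "Complete healing from radiation-induced side effects should have occurred before initiating cabozantinib treatment". That sentence follows directly on a paragraph about cabozantinib in subjects with brain metastases.

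**The concern.** The steroid allowance is written for people in whom radiation has left an effect that still needs treatment. The hemorrhage section, read at face value, says such effects should be gone before cabozantinib is started. Neither passage refers to the other.

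What is at stake is a safety instruction in a small, named group. Section 8.2.4.1.3 acknowledges that the bleeding risk of cabozantinib in subjects with brain metastases has not been fully worked out, and asks for a high level of suspicion for intracranial bleeding. A site that relies on exclusion 5 starts cabozantinib contrary to that section. A site that relies on that section has enrolled an eligible subject who does not begin the planned three-drug regimen on schedule. Two sites could handle the same subject differently, each with a passage in support.

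**Working it through.** There is no stated figure to reproduce. The check sets the passages side by side.

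1. **Who is admitted.** Under exclusion 5 the subject has treated brain metastases, is asymptomatic, takes a stable low dose of dexamethasone, and cannot stop it. The stated reason for not stopping is post-radiation effects. By the criterion's own terms, a radiation effect is present at entry.

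2. **What the safety text asks.** Section 8.2.4.1.3 speaks of complete healing. It sets no grade threshold, does not limit itself to clinically relevant effects, and makes no exception for subjects admitted under exclusion 5.

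3. **Whether timing removes the clash.** It does not. Section 5.1 and the dosing rows of Table 7-1 place the first cabozantinib dose on day 1, together with nivolumab and ipilimumab. No deferred start is described. Exclusion 4 rules out brain radiation only within the 2 weeks before the first dose, so recent radiation is foreseeable.

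4. **Whether inclusion 5 removes it.** Inclusion 5 tolerates residual toxicity that is stable on supportive therapy. That settles entry. It does not speak to the separate condition on starting cabozantinib.

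5. **Whether exclusion 4 is a second contradiction.** Not necessarily. It bars only clinically relevant complications. An effect that causes no symptoms and is stable on a low steroid dose need not be one. The protocol does not define the term or cross-refer to exclusion 5, so the answer is open. If exclusion 4 did catch such a subject, the result would be ineligibility, which is a different outcome from being eligible but unable to start on day 1. The latter can come only from Section 8.2.4.1.3.

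6. **Neurologic wording.** The synopsis asks for neurologically asymptomatic subjects. Section 6.0 explains asymptomatic in parentheses as either no neurologic symptoms or a stable deficit. The fuller text can be taken as defining the shorter one, but a reader of the synopsis alone would not know that a stable deficit is acceptable.

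Result: steps 1 to 4 leave one unresolved conflict, between exclusion 5 and Section 8.2.4.1.3. Steps 5 and 6 leave two points of wording to clarify.

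**The case against.** The strongest reply is that the healing sentence is advisory. It says should, it stands in adverse-event guidance and not among the eligibility criteria, and parts of that guidance are generic: the section discusses squamous lung cancer, and neighbouring sections defer to individual protocols. The section also says that brain metastases of carcinomas are not a contraindication to cabozantinib. Finally, the protocol defines neither post-radiation effects nor radiation-induced side effects, so treating them as the same is an inference.

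Part of this stands. The text does not say must, so calling these subjects untreatable goes further than the documents. But should is also the word this section uses for stopping cabozantinib after life-threatening bleeding, and Section 8.2.4.1 uses it for perforation and severe hemorrhage. It carries the document's main cabozantinib safety directions and cannot be set aside as optional. The statement about contraindication concerns brain metastases as such, not unhealed radiation effects. The undefined terms are a further reason to clarify.

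A reader might also infer harm to the primary analysis, since each subject is 1/14 = 7.1 percentage points of the stage 1 count and 1/23 = 4.3 points of the final rate. The documents do not support that. Those fractions are the weight of any subject and do not measure this conflict. Under Section 7.5, a subject who never receives cabozantinib is not evaluable for response and is replaced. Only a late start would remain, and the documents give no basis for estimating its effect.

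**Conclusion.** The point holds as an inconsistency on a safety matter. Exclusion 5 and Section 8.2.4.1.3 cannot both be followed on day 1 for subjects admitted under the steroid allowance. This rests on one assumption: that an effect which still prevents stopping dexamethasone is not completely healed. That is the plain reading, but the protocol does not state it.

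Two stronger readings are not supported. Exclusion 4 does not clearly contradict exclusion 5, because it is limited to clinically relevant complications and can be read together with inclusion 5. The neurologic wording is a discrepancy between a summary and its fuller definition, not a conflict of rules.

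The number of subjects concerned is not given and cannot be derived from the documents. No effect on the 1-year PFS test, its error rates or the sample size is claimed.

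**What to change.** Reconcile exclusion 5, in both the synopsis and Section 6.0, with Section 8.2.4.1.3, so that one statement says whether a subject admitted under the steroid allowance may start cabozantinib on day 1. The clinical team must choose the rule; this review proposes none.

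In the same amendment:

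- state how the exclusion 4 sentence on ongoing radiation complications applies to these subjects;
- use the same neurologic wording in the synopsis and Section 6.0.

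The cost is a few lines of text in the next amendment. Sample size, decision rules and analysis do not change.

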7.0 STUDY ASSESSMENTS AND PROCEDURES

7.1 Pre-Treatment Period

During the Pre-Treatment Period, subjects are consented and qualified (screened) for the study. Informed consent must be obtained before initiation of any clinical screening procedure that is performed solely for the purpose of determining eligibility for this study. Evaluations performed as part of routine care before informed consent can be considered as screening evaluations if done within the defined screening period, and if permitted by the site's institutional review board (IRB)/ethics committee (EC) policies.

Study eligibility is based on meeting all of the study inclusion criteria and none of the exclusion criteria at screening and on Study Day 1 before study treatment administration. The following assessments will be conducted before subjects receiving their first dose of study drugs on this protocol:

- History and Physical Exam
- Concurrent medication review
- Baseline laboratory assessment
- Baseline EKG
- Staging CT scan chest/abdomen/pelvis (+/- neck) and MRI brain

For each subject, the Pre-Treatment Period ends upon receipt of the first dose of study treatment or final determination that the subject is ineligible for the study.

7.2 Treatment Period

During the Treatment Period subjects will receive nivolumab, ipilimumab and cabozantinib until either disease progression, the occurrence of unacceptable drug-related toxicity or for other reason(s) for subject withdrawal as described in Section 5.2. Treatment will continue for up to 2 years unless there is disease progression, drug intolerance or other reason for discontinuation discussed with the principal investigator (PI). Patients with ongoing complete or partial response may discontinue therapy after 1 year on treatment at the discretion of the treating investigator. Subjects should be instructed to immediately inform the PI/sub-I of any AEs. Subjects experiencing seizures, dizziness, sleepiness, or other symptoms that could influence alertness or coordination should be advised not to drive or operate other heavy machinery.

The following schedule of assessments applies to all subjects (

Table 7-1). More frequent assessments should be obtained if clinically indicated.

Table 7-1: Study Assessments

		Schedule											
		Nivo-Ipi-Cabo combination treatment								Nivo-Cabo treatment		Off treatment but not progressed ⁹	At progression
Cycle Week	Baseline Screening	1	1	4	4	7	7	10	10	13	Q4weeks (weeks 17-105)	Q12 weeks (+/- 4 weeks)	30 day follow up visit
Day of cycle (+/- 3 days)	-14 to 0	1	8	1	8	1	8	1	8	1	1	1	1
Nivolumab dosing q3weeks		X		X		X		X		X	X		
Ipilimumab dosing q3weeks		X		X		X		X					
Cabozantinib dosing continuous		X		X		X		X		X	X		
Medication compliance		X		X		X		X		X	X		
Prior and concomitant medications	X	X		X		X		X		X	X	X	X
Baseline tissue collection ¹	X												
Baseline stool collection		X ⁷											
Physical exam	X	X		X		X		X		X	X	X	X
Vital signs	X	X		X		X		X		X	X	X	X
ECOG PS	X	X		X		X		X		X	X	X	X
Height	X												
Weight	X	X		X		X		X		X	X	X	X
Labs ²	X	X	X	X	X	X	X	X	X	X	X	X	X
Pregnancy test ³	X	X		X		X		X		X	X	X	
12 Lead EKG	X	X		X		X		X		X	X		
Tumor imaging assessments ⁴	X ⁴									X	X ⁶	X ⁶	
Adverse event assessment	X	X		X		X		X		X	X		X
Tumor biopsy ⁵										X			X
Research blood collection ⁸		X		X		X		X					X

1. Baseline tumor collection can be archived specimen if no intervening systemic therapy or fresh biopsy (core needle biopsy, punch biopsy or incisional/excisional biopsy).
2. Labs for Day 1 of each Cycle Week include CBC^a, comprehensive metabolic panel^a, free T3, free T4, TSH, INR/PT, PTT, urinalysis, spot UPCR and Creatine Kinase (CK) with Troponin I if CK is abnormal. Labs for Day 8 of each Cycle Week include only liver

function tests (ALT, AST, alkaline phosphatase, GGT, total protein, albumin, and total bilirubin).

3. Only required for premenopausal female subjects. Urine or blood HCG.
4. CT scan of the chest, abdomen and pelvis. Tumor Imaging Assessments are to be performed within 4 weeks of Cycle 1 Day 1 for the Baseline Screening Assessment. Patients with primary or metastatic disease involving the head or neck areas will require CT scan of the neck as well. MRI brain will be performed at baseline and per discretion of the treating investigator during the treatment period. In patients with a history of a prior brain metastasis, MRI brain will be performed at each reassessment. In patients with active, untreated brain metastases, MRI of the brain should be performed every 6 weeks through week 25 on protocol. Brain imaging with CT scan with IV contrast can be performed in place of MRI brain if there is a contraindication for MRI.
5. Optional core needle biopsy or punch biopsy of superficial tumor in the skin, subcutaneous tissue or lymph node that is palpable on treatment and at progression.
6. Scans every 12 weeks. Scans should occur prior to the visit. A window of -7 to +3 days is acceptable.
7. Patients will need to provide the sample on day 1 of the first cycle (+/- 7 day window).
8. Research blood collection should occur based on the calendar whenever possible and are not required to be redrawn due to treatment delays or interruptions.
9. Follow up off treatment will continue for 2 years after treatment is discontinued. Beyond this time point, progression free survival and overall survival would be assessed every 6 months via chart review or phone contact.

ECG, electrocardiogram; ECOG, Eastern Cooperative Oncology Group; PT/INR, prothrombin time/International Normalized Ratio; PTT, partial prothrombin time; UPCR, urine protein/creatinine ratio

^aLaboratory tests should include a standard hematology panel (CBC, differential, platelets) and chemistry panel (albumin, alkaline phosphatase, ALT, amylase, AST, bicarbonate, bilirubin, blood urea nitrogen, calcium, chloride, creatinine, glucose, lactate dehydrogenase, lipase, magnesium, phosphorus, potassium, sodium, total protein)

If the subject is unable to have a study assessment taken within the defined time window due to an event outside of his or her control (eg, clinic closure, personal emergency, inclement weather, vacation), the assessment should be performed as close as possible to the required schedule. Regular tumor assessments should be performed in accordance to the guidelines in [Section 7.4] to determine if PD is present.

The Treatment Period ends when a subject receives his or her last dose of study treatment; the subject then enters the Post-Treatment Period.

